10.2.1. Serious Adverse Events

A serious adverse event (SAE) is defined as an adverse event that meets **any** of the following criteria:

- Results in death
- Is life-threatening- Note: The term “life-threatening” in the definition of “serious” refers to an event in which the patient was at risk of death at the time of the event. It does not refer to an event, which hypothetically might have caused death, if it were more severe.
- Requires hospitalization or prolongation of existing hospitalization- Note: In general, hospitalization for treatment of a pre-existing condition(s) that did not worsen from baseline is not considered adverse events and should not be reported as SAEs.
- Results in disability/incapacity
- Is a congenital anomaly/birth defect;
- Is an important medical event- Note: Important medical events that may not result in death, be life threatening, or require hospitalization may be considered an SAE when, based upon appropriate medical judgment, they may jeopardize the patient and may require medical or surgical intervention to prevent one of the outcomes listed above. Examples of such medical events include allergic bronchospasm requiring intensive treatment in an emergency room or at home, blood dyscrasias or convulsions that do not result in inpatient hospitalizations, or the development of drug dependency.

By design of this study SAEs that are endpoint events will only be recorded for the endpoint determination and not captured as SAEs. The intention is that the endpoint events are not reported to IRBs as SAEs, unless the IRB requires that these are reported. Investigators should specifically inform their institution/IRB of this plan and confirm whether or not they want the endpoint events reported. By agreement with the US FDA, these endpoints will also not be reported to the US FDA as SAEs; rather they will be reported as endpoint events. Following adjudication if the event is determined to not meet the criteria for an event, the event will be evaluated as an SAE beginning with that day as Day 0.

10.3. Serious Adverse Event Reporting – Procedure for Investigators

10.3.1. Initial Reports

All SAEs occurring from the time of informed consent until 28 days following the last administration of study medication must be reported to the Sponsor or designee **within 24 hours** of the knowledge of the occurrence (this refers to any adverse event that meets any of

the aforementioned serious criteria). SAEs that the investigator considers related to study medication occurring after the 28-day follow-up period will also be reported to the Sponsor or designee.

The investigator is required to submit SAE reports to the Institutional Review Board (IRB) or Independent Ethics Committee (IEC) in accordance with local requirements. All investigators involved in studies using the same investigational medicinal product (IMP) will receive any Suspected Unexpected Serious Adverse Reaction (SUSAR) reports for onward submission to their local IRB as required. All reports sent to investigators will be blinded.

In addition, regulatory agencies will be notified of SAEs per the requirements of the specific regulatory jurisdiction regulations and laws.

10.3.2. Follow-Up Reports

The investigator must continue to follow the patient until the SAE has subsided, or until the condition becomes chronic in nature, stabilizes (in the case of persistent impairment), or the patient dies. Within 24 hours of receipt of follow-up information, the investigator must update the SAE form electronically in the EDC system for the study and submit any supporting documentation (e.g., laboratory test reports, patient discharge summary, or autopsy reports) to the Sponsor or designee via fax or email.

10.3.3. Reporting by the Sponsor

IRBs and IECs will be informed of SUSARs according to local requirements. Cases will be unblinded for reporting purposes as required.

10.4. Exposure *In Utero* During Clinical Trials

If a patient becomes pregnant during the study, the investigator should report the pregnancy to the Sponsor or designee within 24 hours of being notified. The Sponsor or designee will then forward the Exposure *In Utero* form to the investigator for completion.

The patient should be followed by the investigator until completion of the pregnancy. If the pregnancy ends for any reason before the anticipated date, the investigator should notify the Sponsor or designee. At the completion of the pregnancy, the investigator will document the outcome of the pregnancy. If the outcome of the pregnancy meets the criteria for immediate classification as an SAE (i.e., postpartum complication, spontaneous abortion, stillbirth, neonatal death, or congenital anomaly), the investigator should follow the procedures for reporting an SAE.

11. TREATMENT DISCONTINUATION/PATIENT WITHDRAWAL

Patients may withdraw from the study at any time and for any reason. Study drug administration may also be discontinued at any time, at the discretion of the investigator. In any case, follow-up for efficacy and safety should be continued.

11.1. Reasons for Early Study Drug Discontinuation

Study drug discontinuation should be avoided as much as possible, but may be done for any of the following reasons:

- Patient withdraws consent or requests early discontinuation from the study for any reason. Patients should be encouraged to continue to participate in the study for the entire duration of the study even if they choose not to take study medication any longer.
- Occurrence of a clinical or laboratory adverse event, either serious or non-serious, at the discretion of the investigator. The Sponsor or designee should be notified if a patient is discontinued because of an adverse event or laboratory abnormality. It is recommended that, unless clear contraindications arise, patients be strongly encouraged to adhere to their treatment regimen with the study drug for the duration of the trial. Any interruptions of therapy should, if possible, be brief (e.g., <4 weeks) and only for clinically indicated reasons, such as adverse events. The following should be considered reason for discontinuation:
 - ALT > 3x ULN and bilirubin > 1.5x ULN
 - ALT >5x ULN
 - ALT >3x ULN and appearance or worsening of hepatitis
 - ALT > 3x ULN persisting for >4weeks
 - ALT > 3x ULN and cannot be monitored weekly for 4 weeks
- Any medical condition or personal circumstance that, in the opinion of the investigator, exposes the patient to risk by continuing in the study or precludes adherence to the protocol.
- Sponsor discontinues the study.
- A TG value that is flagged as critically high, i.e., >1000 mg/dL (11.29 mmol/L), and confirmed as critically high by a repeat measurement (new fasting blood sample) within 7 days. In this case, a patient may be discontinued from study drug (with the option to remain ODIS) and other lipid-altering medications may be (re)initiated. If the TG value is flagged as >2000 mg/dL (22.58 mmol/L) then appropriate medical action can be taken by the investigator as soon as possible.

Occurrence of an outcome event according to the judgment of the investigator is not considered a valid reason for study drug discontinuation.

Patients whose treatment with study medication is discontinued early, and have not withdrawn consent, will stay in study and will be monitored until the end of the study. Patients that continue in the study after indefinite cessation of therapy will be characterized as Off Drug In Study (ODIS). ODIS patients should be asked to return to the study site for an interim visit once the patient has been off study drug for >30 days. Procedures at this visit are consistent with those at Visit 5. If not contraindicated, patients will also have the option to restart study medication at any point once characterized as ODIS.

The reason for study drug discontinuation or interruption will be recorded on the CRF.

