6.1.2.2. Visit 3 (Day 120; ~4 Months)

Patients will return to the Research Site for Visit 3 on Day 120 ± 10 days.

The following procedures will be performed:

- Perform physical examination
- Obtain weight
- Obtain vital signs (systolic and diastolic blood pressure, heart rate, respiratory rate, and body temperature)
- Obtain fasting blood samples for:
 - Chemistry and hematology testing
 - Lipid profile
- Review study drug compliance by unused capsule count; discuss with and counsel patients about compliance if needed
- Administer study drug - Note: Study drug should be taken orally with food following the collection of all fasting blood samples
- Assess and record efficacy events
- Assess for and record adverse events
- Record concomitant medication(s)
- Instruct patient:
 - To bring all study supplies with them to the next visit
 - Not to take study drug on the morning of their next visit
 - To fast for ≥ 10 hours prior to the next visit

6.1.2.3. Visits 4, 5, 6 and 7

At Visit 4: Day 360 ± 10 ; Visit 5: Day 720 ± 10 ; Visit 6: Day 1080 ± 10 ; and Visit 7: Day 1440 ± 10 , the following procedures will be performed:

- Perform physical examination
- Obtain weight
- Obtain vital signs (systolic and diastolic blood pressure, heart rate, respiratory rate, and body temperature)
- Measure waist circumference (collected at Visit 5 only)
- Obtain a 12-lead electrocardiogram
- Obtain fasting blood samples for:
 - Chemistry and hematology testing
 - Lipid profile
 - Biomarker assays (collected at Visit 5 only)
 - Archiving (in countries and at sites approved by IRB/IEC and dependent on country regulations)

- Review study drug compliance by unused capsule count; discuss with and counsel patients about compliance if needed
- Administer study drug - Note: Study drug should be taken orally with food following the collection of all fasting blood samples
- Assess and record efficacy events
- Assess for and record adverse events
- Record concomitant medication(s)
- Instruct patient:
 - To bring all study supplies with them to the next visit
 - Not to take study drug on the morning of their next visit
 - To fast for ≥ 10 hours prior to the next visit

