11.2. Follow-Up after Early Study Drug Discontinuation/Lost to Follow-Up

- Patients who prematurely discontinue study drug are not to be replaced.
- All randomized patients must be followed up according to the study flowchart until the study end date or death, regardless of whether they discontinue study drug prematurely or not. Any event occurring after early study drug discontinuation will be recorded up through the study end date.

- In order to follow the medical status of the patients, especially when they discontinued the study, investigators are encouraged to obtain information from the patient's primary care practitioner (physician or any other medical care provider). Investigators are also requested to try as much as possible to re-contact those patients at the end of the trial to obtain at least their vital status as well as their status with respect to the primary endpoint, and thus avoid lost to follow-up for the efficacy assessment.
- If patients are lost to follow-up, the CRF must be completed up to the last visit or contact.

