12.1.3. Per-Protocol Population

The per-protocol (PP) population will include all ITT patients without any major protocol deviations, and who had $\geq 80\%$ compliance with study drug while on treatment (up to discontinuation for patients whose treatment is terminated early). The per-protocol efficacy analysis for CV events will be restricted to each patient's time on study drug plus 30 days thereafter.

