12.2.5. Analysis of Safety

All analyses of safety will be conducted on the safety population, which is defined as all randomized patients who receive at least one dose of study drug. The safety assessment will be based on the frequency of adverse events, physical exams, vital signs and safety laboratory tests.

Adverse events with new onset during the study between the initiation of study drug and 30 days after the last dose of study drug for each patient will be considered treatment-emergent (TEAEs). This will include any AE with onset prior to initiation of study drug and increased severity after the treatment initiation.

Treatment-emergent adverse events will be summarized by system organ class and preferred term, and by treatment. This will include overall incidence rates (regardless of severity and relationship to study drug), and incidence rates for moderate or severe adverse events. A summary of SAEs and adverse events leading to early discontinuation from the study will be presented through data listings.

Safety laboratory tests and vital signs will be summarized by post-treatment change from baseline for each of the parameters using descriptive statistics by treatment group. Those patients with significant laboratory abnormalities will be identified in data listings. Additional safety parameters will be summarized in data listings.

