APPENDIX A: SCHEDULE OF PROCEDURES

Study Day	Screening		Follow-Up (FU) ¹³						
	Up to 42 days before Day 0	If a Visit 1.1 takes place, Visit 1 may occur up to 60 days before Day 0 ²	0	120 ± 10	360 ± 10	720 ± 10	1080 ± 10	1440 ± 10	1800 + 30
Months of FU			0	4	12	24	36	48	60
Years of FU			0	0.33	1	2	3	4	5
Visit #	1	1.1	2	3	4	5	6	7	LV ¹⁴
Study Procedures:									
Informed Consent	X								
Medical, Surgical & Family History	X								
Demographics	X								
Evaluate inclusion / exclusion criteria	X ¹	X ³	X						
Physical Examination			X	X	X	X	X	X	X
Weight, Height ⁴	X		X	X	X	X	X	X	X
Vital Signs ⁵	X	X	X	X	X	X	X	X	X
Waist Circumference			X			X			X
12-Lead ECG	X		X		X	X	X	X	X
Urine pregnancy test ⁶	X		X						
Concomitant Meds	X	X	X	X	X	X	X	X	X
Randomization			X						
Dosing at the Research Site ⁷			X	X	X	X	X	X	
Efficacy events				X	X	X	X	X	X
AE Evaluations			X	X	X	X	X	X	X
Compliance Check ⁸				X	X	X	X	X	X
Chemistry and hematology ⁹	X	X ³	X	X	X	X	X	X	X
Fasting lipid profile ¹⁰	X	X ³	X	X	X	X	X	X	X
Genetic testing ¹¹			X						
Biomarkers: hs-CRP, apo B, hsTNT			X			X			X
Fasting blood sample for archiving ¹²			X		X	X	X	X	X

1. Includes procedures and (fasting) blood samples (for example, hs-CRP, calculated creatinine clearance) as needed to determine the CV risk category (see inclusion criteria).
2. Screening visit to re-evaluate inclusion/exclusion criteria for patients who are not eligible for participation based on data from Visit 1.
3. Inclusion/exclusion criteria will be re-evaluated for selected study procedures that are performed on Visit 1.1 because patients failed to meet them at Visit 1.
4. Height at first screening visit only.
5. Vital signs, including systolic and diastolic blood pressure (mmHg), heart rate, respiratory rate and body temperature. Participants must be seated for at least 5 minutes before assessments of vital signs.
6. For women of childbearing potential.
7. The patients will fast of at least 10 hours before arriving at the Research Site, when all fasting blood samples will be obtained. After blood samples are obtained, patients will be given drug with food.
8. Review study drug compliance by unused capsule count, discuss with and counsel patients about compliance if needed; final study compliance at last visit.

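### Amendment 1 counts treatment-emergent events over one unbroken interval per patient, so a restart after more than 30 days off drug makes every adverse event in the gap treatment-emergent

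*Combined protocol and SAP*

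**What the plan says.** All references are to Amendment 1 (16 May 2013).

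- **Window (12.2.5).** An event counts if its onset falls between the start of study drug and a single closing point: "30 days after the last dose of study drug for each patient will be considered treatment-emergent". Interruptions are not mentioned.
- **Restart (11.1).** A patient who has stopped indefinitely but stays in follow-up is classed as Off Drug In Study (ODIS). Provided there is no contraindication, "patients will also have the option to restart study medication at any point once characterized as ODIS".
- **Other drugs while off (7.2.1).** Niacin above 200 mg/day, fibrates, prescription omega-3 products and some others are prohibited, except in ODIS patients with compelling medical reasons. They must be stopped if the patient agrees to restart.
- **Visits for ODIS patients.** Section 11.1 asks for an interim visit after more than 30 days off drug and adds: "Procedures at this visit are consistent with those at Visit 5". The list for Visits 4 to 7 (6.1.2.3) has the same dosing item as Visit 3: "Administer study drug - Note: Study drug should be taken orally with food following the collection of all fasting blood samples". Section 11.2 says: "All randomized patients must be followed up according to the study flowchart until the study end date or death", whether or not drug was stopped. The Appendix A row "Dosing at the Research Site" covers Visits 2 to 7. Neither that row, its footnote, nor section 7.1.1 mentions ODIS patients.

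**The concern.** The protocol expects some patients to have two or more spells on drug, yet the safety window assumes one. A later dose moves the last dose forward, and the window stretches back across the whole time off drug.

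The label on an event then depends on something that happens after it. Take two patients who stop at Day 120 and have the same event at Day 400. If neither restarts, neither event is treatment-emergent. If one restarts at Day 720, that patient's Day 400 event becomes treatment-emergent in retrospect, although exposure when it occurred was the same.

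The gap is also not neutral time. Section 7.2.1 allows lipid drugs in it that are barred on study drug, and section 1.5 lists adverse effects of niacin and fibrates. An event that arises on one of them in the gap would be tabulated as treatment-emergent for the randomized product. What is at stake is whether the adverse event tables by system organ class and preferred term describe time on drug.

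**Working it through.** The plan states no figure on this point, so there is none to reproduce. The check is day arithmetic on the window.

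**Inputs.** The 30-day tail is from 12.2.5. Visit days 360, 720, 1080 and 1440 are from 6.1.2.3. The interim visit after more than 30 days off drug is from 11.1. Assumed: the last dose before the stop falls on day S (120 or 360), followed by one later dose on day R.

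**Formulas.**
- Window closes at S + 30 without the later dose, and at R + 30 with it.
- Off-drug gap G = R − S − 1 days.
- The first min(G, 30) gap days are inside the window in any case, so newly included days N = max(0, G − 30).

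| S | R | Close without | Close with | G | N |
|---|---|---|---|---|---|
| 120 | 151 | 150 | 181 | 30 | 0 |
| 120 | 360 | 150 | 390 | 239 | 209 |
| 120 | 720 | 150 | 750 | 599 | 569 |
| 120 | 1080 | 150 | 1110 | 959 | 929 |
| 120 | 1440 | 150 | 1470 | 1319 | 1289 |
| 360 | 720 | 390 | 750 | 359 | 329 |
| 360 | 1080 | 390 | 1110 | 719 | 689 |
| 360 | 1440 | 390 | 1470 | 1079 | 1049 |

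Cross-check for S = 120, R = 720. The single window runs from Day 0 to Day 750, which is 751 days. Counting each spell plus 30 days gives Days 0 to 150 (151 days) and Days 720 to 750 (31 days), 182 in all. The difference is 751 − 182 = 569.

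The first row is the earliest possible ODIS interim visit after a Day 120 stop. A dose then would add no gap days. The problem arises only with gaps longer than 30 days.

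**Scale across the trial.** The share who restart is not stated. Suppose 1% of 7990, about 80 patients, restart after gaps of 1 to 2 years. Net of the tail, the added time is 80 × (365 − 30)/365 ≈ 73 to 80 × (730 − 30)/365 ≈ 153 patient-years. Against roughly 7990 × 4 = 31,960 planned patient-years, that is about 0.2% to 0.5% for each 1% who restart. Section 12.2.5 reports incidence and names no person-time denominator, so this is only a rough guide to size.

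**The case against.** The best defence is that a continuous window is simple, applies equally to both arms, and picks up delayed harms that appear after a stop. The protocol discourages long interruptions, and any gap of 30 days or less is covered by the tail. Restarts may be few, and on the scale above the added time is a small part of follow-up. Section 12.2 also defers detail to a separate SAP, and only the cover of Amendment 2 is supplied, so a rule for gaps may exist elsewhere.

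Much of this stands. It limits the size of the problem and confines it to long gaps. It does not justify the rule as written. If late harms are the reason for counting gap events, they matter as much in patients who never restart, yet those patients' windows close 30 days after the stop. Equal application to both arms does not make the label accurate, because who restarts, and when, is not randomized.

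A reader might also infer that sites are told to dose patients who have been taken off drug. The documents do not go that far. Restart is conditional on no contraindication and, in 7.2.1, on the patient's agreement. The visit lists and the flowchart lack an exception for ODIS patients, but no sentence directs that they be dosed. The passages conflict on a literal reading and need reconciling. The window problem does not depend on this, because the restart option alone produces it.

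**Conclusion.** The point holds for the text of Amendment 1. Section 12.2.5 gives one interval per patient, section 11.1 allows restart after indefinite cessation, and nothing supplied closes the interval in between. With the assumed Day 120 stop, one later dose at a scheduled visit newly includes from 209 days (Day 360) to 1289 days (Day 1440) off drug. The number of patients affected cannot be derived from the documents.

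Three stronger conclusions are tempting but not supported:

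- **That a true difference between arms is diluted.** This would need event rates and restart patterns in the gaps by arm, which the documents do not give. The direction of any effect is open.
- **That the per-protocol analysis has the same fault.** Section 12.1.3 restricts it to "time on study drug plus 30 days thereafter". That wording does not run to the last dose and, read plainly, leaves out off-drug gaps, although it is unclear about a second spell.
- **That efficacy conclusions are at risk.** The primary analysis population is intent-to-treat and is not limited to time on drug.

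A gap rule in the separate SAP or in the body of Amendment 2 would resolve the window point. Neither could be checked.

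**What to change.** 1. In 12.2.5, define treatment-emergent time as the union of on-drug spells, each running from its start to 30 days after its stop. Tabulate adverse events with onset in longer gaps separately, by arm, as off-treatment.
2. Capture stop and restart dates on the CRF. Section 11.1 requires the reason for a discontinuation or interruption to be recorded there but does not mention dates. Settle the rule before unblinding.
3. Reconcile the ODIS definition (11.1) and the patient-agreement wording (7.2.1) with the Visit 5 cross-reference, 6.1.2.3, 7.1.1 and the Appendix A dosing row, so that one statement, for example an Appendix A footnote, says how site dosing applies to ODIS patients. What that statement should be is a clinical matter for the sponsor.

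**Cost.** A change of wording in 12.2.5, one clarifying footnote, some extra programming and date capture. Delayed harms that arise in a gap leave the treatment-emergent tables, but they remain visible in the off-treatment table. If the separate SAP or Amendment 2 already contains such a rule, a cross-reference in 12.2.5 is enough for item 1.

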11.2. Follow-Up after Early Study Drug Discontinuation/Lost to Follow-Up

- Patients who prematurely discontinue study drug are not to be replaced.
- All randomized patients must be followed up according to the study flowchart until the study end date or death, regardless of whether they discontinue study drug prematurely or not. Any event occurring after early study drug discontinuation will be recorded up through the study end date.

- In order to follow the medical status of the patients, especially when they discontinued the study, investigators are encouraged to obtain information from the patient's primary care practitioner (physician or any other medical care provider). Investigators are also requested to try as much as possible to re-contact those patients at the end of the trial to obtain at least their vital status as well as their status with respect to the primary endpoint, and thus avoid lost to follow-up for the efficacy assessment.
- If patients are lost to follow-up, the CRF must be completed up to the last visit or contact.

